Study Protocol

TJ-IRB202411010

**Retrospectively Analyze the
Correlation Between Body
Composition Based on CT
Measurement and Pathological
Grading and Prognosis in Patients
with Gastroenteropancreatic
Neuroendocrine Neoplasms**

Version date: 2024.11.4

I. Research Background

Neuroendocrine Neoplasms (NENs) are a heterogeneous group of tumors. Although relatively rare, their incidence has increased rapidly over the past decade (1). NENs can occur in any organ or tissue, with 62-70% occurring in the gastrointestinal-pancreatic system (GEP-NENs)(2).

According to the WHO classification criteria, NENs are divided into well-differentiated gastroenteropancreatic neuroendocrine tumors (GEP-NETs), poorly differentiated gastroenteropancreatic neuroendocrine carcinomas (GEP-NECs), and mixed neuroendocrine/neuroepithelial tumors (MiNENs). Based on the Ki-67 proliferation index and/or mitotic count, GEP NET is classified into grades G1, G2, and G3. GEP NET G3, GEP NEC, and MiNENs are considered high-grade GEP NENs, while NET G1 and NET G2 are considered low-grade GEP NENs(3,4). Treatment for high-grade and low-grade neuroendocrine tumors differ(5). Patients with high-grade neuroendocrine tumors tend to have shorter median overall survival and poorer prognosis(6). Therefore, pathological grading is of great significance for clinical diagnosis, treatment, and prognosis of patients. However, most information can only be obtained after surgical and histological evaluation(7). Thus, exploring markers associated with GEP-NENs grading and prognosis is of great importance for patient diagnosis and treatment.

Excess body fat is one of the causes of various cancers. Studies have shown that BMI is a risk factor for neuroendocrine tumors(9). Although BMI is used to assess obesity, it does not specifically reflect the distribution of body fat or distinguish between muscle and fat tissue (10). Computed tomography (CT) can economically and effectively obtain body composition parameters such as muscle and fat(11). Recently, CT images at the third lumbar level have been considered a widely available method and have been used to study body composition in several diseases(12-14). However, two-dimensional parameters have their limitations: cannot explain differences in fat and muscle distribution among individuals. Prognostic analysis using three-dimensional body composition parameters is relatively rare.

In this study, we attempted to explore the relationship between 3D body

composition parameters and grading and prognosis of NENs through a larger sample size.

II. Research Objectives

This study aims to analyze the association between body composition measured by CT and the pathological grading and prognosis of patients with GEP-NENs confirmed by surgical pathology through a retrospective review of CT imaging data..

III. Research Design

This study is a retrospective study.

IV. Selection of subjects

1. Inclusion criteria

- (1) a confirmed diagnosis of GEP-NENs via histopathology with a WHO grading.
- (2) available enhanced CT scans that included full abdominal imaging before surgery or biopsy.

2. Exclusion criteria

- (1) therapeutic interventions before surgery or biopsy
- (2) poor image quality or incomplete CT images of the whole abdomen.

V. Sample size

Retrospective analysis of GEP-NENs patients from 3 Hospitals from April 2014 to April 2024. The number of included cases was 633 patients.

VI. Research process

1. Clinical Data Collection: Through the Radiology Information System (RIS) , we queried the list of patients with GEP-NENs from April 2014 to April 2024. Based on postoperative pathology and imaging examination types, combined with the exclusion criteria of this study, clinical cases were screened.
2. Collection of imaging data: Use PACS system to sort out the patient's imaging data information through inclusion and exclusion criteria, screen the cases that can be enrolled.

3. Image data processing: Through PACS system, DICOM format image data is downloaded by workstation, and the image is post-processed and analyzed on the computer with image post-processing software.

VII. Statistical analysis

Data are presented as medians (range) or number (proportion). The Shapiro-Wilk test for normality is employed. Depending on their distribution, Mann-Whitney U or student t tests are performed. We conduct univariate logistic regression analysis to evaluate the relationship between certain variables and a high grade of GEP-NENs. Variables with $p<0.05$ are chosen for multivariate analysis, for which odds ratios (ORs) with 95% confidence intervals (CIs) are computed. The optimal cut-off of continuous variables are obtained by using X-tile. A univariate and multivariable Cox proportional hazard model is constructed to determine predictive factors for prognosis. PFS and OS are estimated using the Kaplan-Meier method and compared by the log-rank test. Statistical analyses are conducted using SPSS (version 26.0, IBM) and GraphPad Prism (version 8.3.0, GraphPad Software Inc., USA), with a significance threshold of $p<0.05$

References

1. M. Pavel et al., Gastroenteropancreatic neuroendocrine neoplasms: ESMO Clinical Practice Guidelines for diagnosis, treatment and follow-up. *Ann Oncol* 31, 844-860 (2020).
2. J. M. Fang, J. Li, J. Shi, An update on the diagnosis of gastroenteropancreatic neuroendocrine neoplasms. *World J Gastroenterol* 28, 1009-1023 (2022).
3. X. X. Mao, J. Chen, [Interpretation on the update of 2022 WHO classification of neuroendocrine tumors]. *Zhonghua Bing Li Xue Za Zhi* 53, 655-659 (2024).
4. I. D. Nagtegaal et al., The 2019 WHO classification of tumours of the digestive system. *Histopathology* 76, 182-188 (2020).
5. T. Ito et al., JNETS clinical practice guidelines for gastroenteropancreatic neuroendocrine neoplasms: diagnosis, treatment, and follow-up: a synopsis. *J Gastroenterol* 56, 1033-1044 (2021).
6. A. Dasari et al., Trends in the Incidence, Prevalence, and Survival Outcomes in Patients With Neuroendocrine Tumors in the United States. *JAMA Oncol* 3, 1335-1342 (2017).
7. G. Chiti et al., Gastroenteropancreatic neuroendocrine neoplasms (GEP-NENs): a radiomic model to predict tumor grade. *Radiol Med* 127, 928-938 (2022).
8. T. Byers, R. L. Sedjo, Body fatness as a cause of cancer: epidemiologic clues to biologic mechanisms. *Endocr Relat Cancer* 22, R125-134 (2015).
9. E. Leoncini, G. Carioli, C. La Vecchia, S. Boccia, G. Rindi, Risk factors for neuroendocrine neoplasms: a systematic review and meta-analysis. *Ann Oncol* 27, 68-81 (2016).

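### No hospital covariate or stratum is pre-specified for three pooled hospitals, so hospital differences in both body composition and outcome could produce spurious associations

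*Combined protocol and SAP*

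**What the plan says.** Section V states the source of the patients ("Retrospective analysis of GEP-NENs patients from 3 Hospitals from April 2014 to April 2024") and the total ("The number of included cases was 633 patients"). It gives no number per hospital.

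Section VII is the whole analysis plan:

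- Two-group comparisons: "Depending on their distribution, Mann-Whitney U or student t tests are performed".
- Grade: "We conduct univariate logistic regression analysis to evaluate the relationship between certain variables and a high grade of GEP-NENs". The candidate variables are not listed. The entry rule is "Variables with $p<0.05$ are chosen for multivariate analysis".
- Cut-offs: "The optimal cut-off of continuous variables are obtained by using X-tile", with no mention of hospital.
- Prognosis: "A univariate and multivariable Cox proportional hazard model is constructed to determine predictive factors for prognosis". No covariates, entry rule or strata are given.
- Survival curves: "PFS and OS are estimated using the Kaplan-Meier method and compared by the log-rank test". No stratification is mentioned.

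Hospital, centre or site does not appear in section VII as a covariate, stratum, cluster or sensitivity analysis. Section VI describes one image-processing workflow. It does not describe any step to align CT acquisition across the hospitals.

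**The concern.** The exposure is an image measurement and the outcomes are tumour grade, PFS and OS. Hospitals may differ in the patients referred to them, in survival and follow-up, and in how CT is acquired. If they differ both in the body-composition value and in grade or prognosis, hospital is a common cause of the two. A pooled comparison then mixes the between-hospital difference with the patient-level association that the study wants to estimate. A reader of the pooled results, with nothing shown by hospital, could not tell the two apart.

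The stake is the study's main product: odds ratios, hazard ratios and p-values for body-composition parameters.

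**Working it through.** **No planned figure to reproduce.** The 633 is a count of available patients. It has no stated effect size, power, event rate or hospital split behind it.

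**Inputs from the protocol:** 3 hospitals, 633 patients, threshold 0.05. **Assumptions:** two-sided tests; 211 patients per hospital (633/3); body composition with SD 1 inside each hospital; no association inside any hospital; high-grade shares and hospital means as stated below.

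**Hand approximation for the pooled two-group comparison.** Let Δ be the expected difference in mean body composition between high and low grade that arises only from hospital mix.

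Shares 20/30/40%, means 0/0.25/0.5 SD:

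- Mean in high grade = (0.2×0 + 0.3×0.25 + 0.4×0.5)/0.9 = 0.275/0.9 = 0.3056
- Mean in low grade = (0.8×0 + 0.7×0.25 + 0.6×0.5)/2.1 = 0.475/2.1 = 0.2262
- Δ = 0.0794 SD
- Between-hospital variance = (0.25² + 0 + 0.25²)/3 = 0.0417, so the pooled SD = √1.0417 = 1.021
- Expected numbers: high 211×0.9 = 189.9, low 211×2.1 = 443.1
- SE = 1.021×√(1/189.9 + 1/443.1) = 0.0885
- δ = Δ/SE = 0.897
- Rejection rate = Φ(−1.96+δ) + Φ(−1.96−δ) = 0.144 + 0.002 = 14.6%
- Approximate spurious odds ratio per SD = exp(0.0794/1.0417) = 1.08

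Reversing the order of the means only changes the sign of Δ, so the rate is the same. In the other four orderings |Δ| is halved. For means 0/0.5/0.25, for example, Δ = 0.25/0.9 − 0.5/2.1 = 0.0397, δ = 0.448, and the rate is 0.065 + 0.008 = 7.3%.

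**Set against simulation** (logistic regression, 1,000 to 2,000 datasets per scenario; 1,500 for the other orderings):

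| Shares; means | By hand | Simulated, pooled | Simulated, hospital term |
|---|---|---|---|
| 20/30/40%; 0/0.25/0.5 | 14.6% | 12.9% to 14% | 4.6% to 5% |
| 20/30/40%; same spread, other orderings | 7.3% | about 7% to 8.6% | – |
| 20/30/45%; 0/0.25/0.5 | 19.7% | 20% to 20.4% | 4.8% to 5% |
| 25/30/35%; total spread 0.25 | 5.6% | about 5% to 6.3% | about 5% to 5.6% |

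The Mann-Whitney test behaves like the logistic model: 13.5% in the first row and 20.1% in the third.

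**Wider range** (3,000 datasets per scenario, shares 20/30/40%). With 211 per hospital, total spreads of 0.4, 0.6 and 1.0 SD give 11.0%, 17.4% and 40.7%. With hospitals of 433/100/100 they give 10.7%, 16.3% and 33.6%. If hospitals differ only in grade mix or only in body composition, Δ = 0 and the simulated rate is 4.3% to 5.4%. With a hospital term the rate was 4.2% to 5.8% throughout.

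**Cox model.** Assumed hazards of 0.06/0.08/0.12 per year, the same 0.5 SD spread and uniform censoring between 0.5 and 10.5 years give 13.3% to 15% pooled, against about 5% when stratified by hospital (1,000 datasets per run).

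**The case against.** **The covariates are unlisted.** A reader might infer that no model will contain hospital. The protocol does not support that: hospital could be among the unnamed candidates. If it were, the plan's own p<0.05 screen would keep it in about 99% of datasets at shares of 20/30/40%, and most of the inflation in the multivariable logistic model would go. This stands, and it limits the finding to the absence of pre-specification. It does not remove the finding. Hospital is not named, the two-group, univariate and log-rank analyses would still ignore it, and no entry rule is given for the Cox model. At shares of 25/30/35% hospital passes the screen only about half the time, although inflation is also small there.

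**The size depends on the assumptions.** The larger figures need hospitals to differ in both respects and in matching or opposite order. A spurious odds ratio of 1.08 per SD is small, and clinical covariates in the multivariable model might absorb some case mix. All of this stands.

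**The measurement route is partly limited.** The protocol requires enhanced full-abdomen CT, excludes poor images and describes one processing workflow. It does not report scanner differences, so a CT shift between hospitals is a possibility only.

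**The study is exploratory.** That argues for a light remedy. Adjusting every univariate screen, or replacing the descriptive two-group tests by stratified rank tests, would be more than is needed.

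**Conclusion.** The point holds as a gap in pre-specification. Three hospitals are pooled, section VII names no hospital covariate or stratum, and several of its analyses cannot take hospital into account as written. With equal hospitals, shares of 20/30/40% and a 0.5 SD spread in the same or the opposite order, the false-positive rate is about 13–14% instead of about 5%. With other orderings it is about 7%. With mild differences, or differences in only one of the two, it is near 5–6%.

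The mechanism is certain, but its size in this study is unknown, because hospital sizes, shares and means are all assumed. Two further inferences should not be drawn. One is that pooling has been shown to hide or reverse a real association: the calculations cover only the case of no association within hospitals. The other is that the protocol confirms hospital is recorded for every patient: it is likely, given how the cases were assembled, but not stated.

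The plan should be changed because the remedy is cheap and settles in advance whether to adjust. Nothing here shows the planned results to be invalid.

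**What to change.** Add to section VII:

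- Hospital (three levels) enters every multivariable logistic model as a fixed categorical term, whatever its p-value.
- Cox models and log-rank tests for PFS and OS are stratified by hospital.
- Body composition, grade distribution and the main estimates are also reported by hospital, as a sensitivity check.

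The two-group and univariate analyses can stay as they are if they are labelled descriptive. With only three hospitals, a fixed term or strata is preferable to a random effect.

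The cost is two degrees of freedom in the logistic models, slightly wider intervals, a few sentences in the plan and a few lines of SPSS syntax. No new patients are needed. The authors should confirm that hospital can be identified for each patient. If the hospitals turn out to be alike, the results will barely change.

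### The two-group test is chosen by distribution alone; if the grade groups differ in both size and spread, Student's t will not hold 5%, and Welch's t would at almost no cost

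*Combined protocol and SAP*

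**What the plan says.** Section VII (Statistical analysis) states: "The Shapiro-Wilk test for normality is employed". The next sentence gives the consequence: "Depending on their distribution, Mann-Whitney U or student t tests are performed". The significance threshold is 0.05; whether it is two-sided is not stated.

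The section does not say which groups or variables these tests compare, at what level normality is tested, or whether it is tested per group or on pooled data. It mentions no variance check and no unequal-variance form of the t test.

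Three other places bear on the point:

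- Section I defines the natural two-group split: "GEP NET G3, GEP NEC, and MiNENs are considered high-grade GEP NENs, while NET G1 and NET G2 are considered low-grade GEP NENs".
- Section V gives the only sample figure: "The number of included cases was 633 patients". No split by grade and no SD appears anywhere.
- Section VII assigns the formal analysis of grade to regression: "We conduct univariate logistic regression analysis to evaluate the relationship between certain variables and a high grade of GEP-NENs". The odds ratios come from the multivariate logistic model, and entry to it is by p-value after the univariate logistic step.

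**The concern.** Student's t pools the two sample variances. When groups are of unequal size, the pooled variance is dominated by the larger group. If the smaller group is the more variable, the standard error is too small and the test rejects too often. If it is the less variable, the test rejects too rarely. A check of normality does not address this, because two perfectly normal samples can have different SDs.

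The study is retrospective and takes cases as they come, so nothing in the plan makes the grade groups equal in size. Nothing in it suggests that muscle and fat measures have the same spread in both grades either. What is at stake is the unadjusted p-value for each body composition measure between grade groups. Its error rate could lie above or below 5%, in a direction that cannot be known beforehand.

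**Working it through.** The plan states no error-rate or power calculation, so there is no figure of its own to reproduce. The check asks how far Student's t moves from 5% under stated assumptions.

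**Inputs from the documents.** N = 633 (section V); threshold 0.05 (section VII), taken as two-sided; Student's t as the parametric test (section VII).

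**Assumptions, not in the documents.** The groups are high versus low grade. The high-grade share is 15%, 20% or 30%, giving 95 vs 538, 127 vs 506 and 190 vs 443. The high-to-low SD ratio r is 0.75, 1, 1.25 or 1.5.

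**Formula.** With the low-grade SD set to 1, n1 high-grade and n2 low-grade patients:

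- True variance of the mean difference: V_true = r²/n1 + 1/n2
- Variance that Student's t uses: V_pooled = [((n1 − 1)r² + (n2 − 1))/(n1 + n2 − 2)] × (1/n1 + 1/n2)
- Large-sample type I error: 2 × [1 − Φ(1.96 × √(V_pooled/V_true))]

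**Worked case, 127 vs 506, r = 1.5.**

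- V_true = 2.25/127 + 1/506 = 0.01969
- Pooled variance = (126 × 2.25 + 505)/631 = 1.2496
- V_pooled = 1.2496 × (1/127 + 1/506) = 0.01231
- V_pooled/V_true = 0.625, so the effective critical value is 1.96 × √0.625 = 1.55
- Type I error = 12.1%

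**Same split, r = 0.75.** V_true = 0.006405, V_pooled = 0.008990, ratio 1.4035, effective critical value 2.32, type I error 2.0%.

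**All cells, Student's t.**

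| High vs low | r = 0.75 | r = 1 | r = 1.25 | r = 1.5 |
|---|---|---|---|---|
| 95 vs 538 | 1.7% | 5.0% | 9.3% | 13.7% |
| 127 vs 506 | 2.0% | 5.0% | 8.6% | 12.1% |
| 190 vs 443 | 2.8% | 5.0% | 7.3% | 9.3% |

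The r = 1 column shows that unequal size alone does no harm. With a 50:50 split the error is 5.0% at every ratio, so unequal spread alone does none either. Both are needed.

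**Welch's t.** In simulations with normal data (4,000 runs per cell, shares 15% to 30%, ratios 0.67 to 1.5), its error was 3.9% to 5.3%, which is about 5%. With equal spreads at 127 vs 506, simulated power was 80.9% for Welch against 81.2% for Student, a loss of 0.3 points.

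**The full two-stage rule.** At 95 vs 538 on normal data, choosing the test by Shapiro-Wilk gave these simulated error rates:

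| Shapiro-Wilk run | SD ratio 0.67 | SD ratio 1.5 |
|---|---|---|
| On pooled data | 0.9% | 11.2% |
| Per group | 1.0% | 13.5% |

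The pre-test therefore does little to protect the t test. When both groups had identical distributions (normal, gamma or lognormal), the two-stage rule gave 4.3% to 5.3%, so the pre-test by itself caused no inflation.

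**Reach of the t-test branch.** With mild skew (gamma, shape 20), Shapiro-Wilk run per group rejected normality in at least one group in 97% to 98% of samples. Such measures would nearly always go to Mann-Whitney U. On normal data with unequal spreads, Mann-Whitney had error of 2.8% to 8.1% at 127 vs 506. That is closer to 5% than Student's t, but not at 5%.

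**The case against.** The strongest reply is that every departure from 5% rests on two quantities the documents do not give: the grade split and the SD ratio. A reader might infer from the table that the planned test has an error rate of 2% to 14%. The documents do not support that. The range describes what happens across assumed splits and ratios, and nothing in the plan shows that spreads differ by as much as 1.5-fold. This stands, and the figures must be read as conditional.

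A reader might also infer that the normality pre-test is at fault. It is not shown to be: with identical distributions the two-stage rule holds its level. Removing the pre-test for consistency across measures is a reasonable preference, not the repair of a demonstrated error. An analysis on the log scale is likewise a choice, and it would change the target from arithmetic to geometric means.

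Further, skewed measures would mostly go to Mann-Whitney, so Student's t may be applied to few variables. This also stands. It narrows the problem without removing it, since Mann-Whitney is itself off 5% when spreads differ.

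Finally, the main results do not depend on these tests. Grade is analysed by logistic regression, and entry to the multivariate model follows that regression. Prognosis is analysed by Cox models and the log-rank test. To conclude that the odds ratios or hazard ratios are compromised would go beyond the plan's text.

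The central point survives. The plan names the equal-variance test, gives no reason to expect equal variances, and passes over an alternative that is about as powerful when they are equal and valid when they are not.

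**Conclusion.** The concern holds in conditional form, and it is minor. Section VII selects the two-group test by distribution alone and makes no provision for unequal spread. If the comparison is high versus low grade and the groups differ in both size and SD, Student's t does not hold 5%. With a 15% to 30% high-grade share among 633 patients, its error is about 1.7% to 2.8% at an SD ratio of 0.75, 7% to 9% at 1.25 and 9% to 14% at 1.5. It is 5.0% when the SDs are equal. Welch's t stays at about 5% throughout.

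The groups compared are inferred, and the split and SDs are assumed. The consequence is confined to unadjusted two-group p-values for measures that reach the t-test branch.

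**What to change.** In section VII, replace Student's t with Welch's unequal-variance t test for continuous two-group comparisons, and name the groups and variables compared. Preferably make Welch's t the one prespecified test for all continuous measures, so that the method does not vary from measure to measure with the pre-test result. Mann-Whitney U can then be reported for every measure as a sensitivity check, with a note that it too departs from 5% when spreads differ.

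The cost is a sentence or two in the plan. SPSS, the planned software, already prints the unequal-variance result. The statistical price is a power loss of under 1 percentage point if the spreads turn out equal.

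### PFS and OS cut-offs appear to be chosen and tested in the same 633 patients, with no correction for the search

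*Combined protocol and SAP*

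**What the plan says.** Section II makes prognosis one of two aims: "This study aims to analyze the association between body composition measured by CT and the pathological grading and prognosis of patients with GEP-NENs". Section V describes a single series: "Retrospective analysis of GEP-NENs patients from 3 Hospitals from April 2014 to April 2024", and "The number of included cases was 633 patients".

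Section VII gives one way of grouping continuous variables: "The optimal cut-off of continuous variables are obtained by using X-tile". The next two sentences are the survival analyses: "A univariate and multivariable Cox proportional hazard model is constructed to determine predictive factors for prognosis" and "PFS and OS are estimated using the Kaplan-Meier method and compared by the log-rank test". The threshold for all tests is p<0.05.

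No section mentions a training and validation split, a hospital held back, cross-validation, a cut taken from the literature or fixed beforehand, or a p-value adjusted for the search. The plan also leaves open which variables are cut, which endpoint the search optimises, how many cut-offs are allowed, and whether the Cox model takes the grouped or the continuous variable.

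**The concern.** A log-rank test has its stated 5% level when the groups are fixed without looking at the outcome. An optimal cut-off is the best of many candidates. If the criterion is the survival difference in these patients, the reported statistic is the largest of many correlated statistics but is judged as if it were the only one. The p-value is then too small, the hazard ratio at the chosen cut is biased away from 1, and the cut-off is unlikely to reproduce.

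The Cox models are the plan's stated means of identifying prognostic factors. A body-composition parameter unrelated to PFS or OS could therefore be reported as prognostic much more often than one time in twenty. This is per parameter and per endpoint, before any multiplicity across parameters or across PFS and OS.

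The logistic regression for grade, and a Cox model with continuous parameters, are outside this point.

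**Working it through.** **Inputs from the plan.** N = 633; threshold 0.05 (two-sided assumed); ordinary log-rank and Cox tests. The plan gives no event count or power calculation, so there is no figure of its own to reproduce.

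**Assumed, not in the plan.** 15–50% events; one cut-off; the search window and grid; the cut searched on the tested endpoint in the same patients.

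**Step 1: closed form.** For the largest log-rank statistic over cuts between percentiles ε₁ and ε₂, the Miller–Siegmund approximation is

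P(max|Z| ≥ b) ≈ 4φ(b)/b + φ(b)(b − 1/b) ln[ε₂(1 − ε₁)/((1 − ε₂)ε₁)].

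At b = 1.96, φ(b) = 0.0584, so the first term is 0.119 and the multiplier of the logarithm is 0.0847.

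- 10th–90th: 0.119 + 0.0847 × ln 81 (4.394) = 0.49
- 20th–80th: 0.119 + 0.0847 × ln 16 (2.773) = 0.35
- 30th–70th: 0.119 + 0.0847 × ln 5.44 (1.695) = 0.26

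The approximation can run high at so low a threshold, so it was checked by simulation. Solving for a true 5% gives b = 3.054, 2.903 and 2.750, that is, nominal p of 0.0023, 0.0037 and 0.0060.

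**Step 2: unadjusted log-rank, no effect of the parameter.** 2000 runs per setting, exponential survival, 15/30/50% events.

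| Search | Rejection at p<0.05 |
|---|---|
| Every rank, 10th–90th | 44–48% |
| Every rank, 20th–80th | 33–38% |
| Every rank, 30th–70th | 25–28% |
| 7 decile cuts | 18–21% |
| 3 quartile cuts | 12–14% |
| 2 tertile cuts | 9–10% |
| Fixed median | 4–5% |

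A separate simulation with different follow-up, 10–50% events and every fourth rank searched gave 40–42%, 30–32% and 21–24% for the three windows. Searching every second percentile gave 33–38%, 26–30% and 19–22%. Grid density is a plausible reason for the gap.

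**Step 3: Cox at the chosen cut, adjusted for one binary factor.** The factor stands for something like grade (30% prevalence assumed). Ranges cover the three every-rank windows.

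| Shift of parameter by factor | Factor HR 4 | Factor HR 10 |
|---|---|---|
| 0 | 20–40% | 16–34% |
| 0.25 SD | 17–37% | 11–24% |
| 0.5 SD | 13–26% | 9–19% |
| 0.8 SD | 11–20% | 8–15% |

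With a coarse search and a 0.5 SD shift (both HRs): deciles 8–15%, quartiles 5–10%, tertiles 5–8%. With the parameter continuous, adjusted Cox rejects 4–6% throughout.

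**Step 4: cut chosen on one endpoint, tested on the other.** Under an assumed progression-then-death model with every-rank windows, rejection is 7–9% with PFS/OS events of 61/15%, 10–13% with 61/29% and 17–30% with 61/47%. The searched endpoint keeps 24–47%.

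**Step 5: hazard ratio at the chosen cut.** Median fitted HR, taken away from 1, when the truth is 1 (every-rank windows):

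| Events | Chosen cut | Fixed median | Chosen cut, adjusted (factor HR 4, 0.5 SD) |
|---|---|---|---|
| 50% | 1.20–1.30 | 1.08 | 1.12–1.17 |
| 30% | 1.27–1.41 | 1.10 | 1.16–1.24 |
| 15% | 1.39–1.61 | 1.16 | 1.27–1.44 |

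**Step 6: do the remedies hold 5% under the null?** Miller–Siegmund p-value: 4.2–5.1%. Cut chosen in one half and tested in the other: 4.3–5.9%; a separate run of 3000 gave 5.1% in the testing half against 40.3% in the choosing half. Continuous Cox: 4.7–4.9% with 10,000 runs (one run of 1500 gave 7.1%, which was not reproduced).

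**The case against.** **The premise is inferred.** The X-tile sentence sits between the logistic and the Cox sentences and names no outcome, patients or number of cuts. That is correct, and the inflation is therefore stated conditionally. But the plan describes one data set, log-rank needs groups, and no other source of groups is given. If something else is intended, the plan should say so.

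**The largest figures belong to the unadjusted log-rank.** The Cox models are what identify prognostic factors, and adjustment reduces the excess, more so if body composition is related to grade, which is the study's other hypothesis. This stands in part: with quartile or tertile searches and a 0.5 SD shift, rejection falls to 5–10%. With a fine search it stays at 8–40%. The univariate Cox and log-rank analyses are also planned, and adjustment gives them no relief. Only one binary covariate was simulated; a real multivariable model could differ either way.

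**The size depends on unseen choices.** It does: window, grid, event fraction and strength of grade are all assumed. The direction is robust, but no single percentage should be quoted as the trial's error rate.

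**The closed-form correction is partial.** Accepted. It covers one cut and the unadjusted log-rank statistic, not a two-cut grouping or the multivariable Cox p-value. Its thresholds are approximate; simulation gives 0.0022–0.0031, 0.0037–0.0049 and 0.0053–0.0078 for the three windows.

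**The study is exploratory and retrospective.** That lowers the consequence of an error, but it does not make a p-value read against 0.05 valid.

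**Conclusion.** The concern holds and the plan should be changed before results are reported. As written, the method searches for the best cut and then applies ordinary tests, with no stated protection.

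If the same patients and endpoint choose and test one cut-off, a parameter with no effect is significant on the unadjusted log-rank test in about 19–48% of studies with a fine search (the range covers the windows and grids tried) and 9–21% with a coarse one, against 5% nominal. Adjusted Cox results range from about 5% to 40%, depending on the grid and on how strongly the parameter and the outcome depend on grade. The endpoint not used for the search is affected less, at 7–30%. These are per parameter and endpoint, and rest on the assumed 15–50% events (10–50% in the separate simulation), the search windows and the other inputs listed above.

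**What to change.** 1. Make the inferential PFS and OS analysis a Cox model with each body-composition parameter continuous, for example HR per SD, allowing for non-linearity.
2. Keep X-tile groups for descriptive Kaplan–Meier curves.
3. If a p-value at a cut-off is reported, either use one corrected for maximal selection, or choose the cut in a pre-specified subset and test it once in the remaining patients. The closed form suits only a single cut on the unadjusted log-rank statistic.
4. State which variables are cut, in which patients and on which endpoint.

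The cost is a few sentences, a little computation and no new data. The closed-form correction needs only the largest log-rank statistic and the search window. Some cut-off p-values will become less favourable.

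Simulated power for an assumed linear HR of 1.3 per SD, N = 633:

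| Analysis | 15% events | 30% events | 50% events |
|---|---|---|---|
| Continuous Cox | 71% | 95% | >99% |
| Corrected best cut, 20th–80th | 57% | 87% | 97% |
| Cut chosen in half, tested in the other half | 27% | 48% | 69% |

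Under a linear effect the continuous analysis is therefore also the most powerful of the three, and splitting is the expensive option.

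### Does the crude log-rank comparison, with no commitment to grade in the Cox model, undermine the survival analysis?

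*Combined protocol and SAP*

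**What the plan says.** The survival plan in section VII (Statistical analysis) has two sentences on modelling and testing. One reads "A univariate and multivariable Cox proportional hazard model is constructed to determine predictive factors for prognosis". The other reads "PFS and OS are estimated using the Kaplan-Meier method and compared by the log-rank test". Neither names strata, covariates or the groups compared. The p<0.05 rule for carrying variables forward is written for the model that yields odds ratios, that is, the logistic model for high grade; it is not stated for the Cox model. Shortly before, the section adds that "The optimal cut-off of continuous variables are obtained by using X-tile", which suggests, without saying so, that the log-rank groups are body-composition groups.

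Section II (Research Objectives) sets the aim as the "association between body composition measured by CT and the pathological grading and prognosis of patients with GEP-NENs". Section I (Research Background) says that high-grade disease has worse survival and is treated differently from low-grade disease. Section IV requires "a confirmed diagnosis of GEP-NENs via histopathology with a WHO grading", so grade is known for every patient. Section V gives a count of available cases: "The number of included cases was 633 patients".

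**The concern.** The protocol itself supplies both arms of a confounding triangle. Grade predicts survival (section I), and a link between body composition and grade is half of the objective (section II). If that link is found, a crude log-rank difference between body-composition groups carries part of the grade effect. If the link runs the other way, a real difference within grade may be hidden. Because nothing commits the Cox model to grade, a reader may fear that a crude difference will be reported as an independent prognostic factor, or that a true one will be missed.

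**Working it through.** The plan has no power or effect figure to reproduce. Only n = 633 and the 0.05 threshold come from the documents. Assumed: two equal marker groups with a fixed cut-off, two-sided testing, 20-40% high grade, grade hazard ratio (HR) 2, 3 or 6, and 30% of patients with an event, i.e. 0.30 × 633 ≈ 190.

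**1. How strong a marker-grade link is relevant?** Take the link that the grade analysis could detect with 80% power, at about 316 per group. With 30% high grade overall, an odds ratio (OR) of 1.63 corresponds to 35.1% against 24.9% high grade in the two groups: (0.351/0.649)/(0.249/0.751) = 1.63. The pooled two-proportion formula gives

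z = [0.102·√316 − 1.96·√(2·0.3·0.7)] / √(0.351·0.649 + 0.249·0.751) = 0.84, so power is 80%.

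At 20% and 40% high grade the corresponding ORs are 1.76 and 1.58.

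**2. How much grade effect leaks into the crude comparison?** With no effect within grade, the crude HR at the start of follow-up is (1 + 0.351(h − 1)) / (1 + 0.249(h − 1)), where h is the grade HR. Later it shrinks, as high-grade patients have their events sooner. The approximate rejection rate uses the Schoenfeld shift √190/2 × ln(HR) = 6.892 × ln(HR). The simulated column is the crude log-rank test at 30% high grade, 4,000 replicates per setting, with exponential survival.

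| Grade HR | Initial crude HR | Shift | Approximate rejection | Simulated rejection |
|---|---|---|---|---|
| 2 | 1.351/1.249 = 1.08 | 0.54 | 8.4% | 7.6% |
| 3 | 1.702/1.498 = 1.14 | 0.88 | 14.2% | 13.1% |
| 6 | 2.755/2.245 = 1.23 | 1.41 | 29.2% | 26.5% |

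The approximation runs slightly high because it uses the initial HR. Across 20-40% high grade, the simulated crude rates are 7-8%, 12-13% and 25-27%. The grade-stratified test gives 4.6-5.7%. With no marker-grade link, the crude test rejects 4-5%.

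**3. The opposite direction.** With a true within-grade HR of 1.5, 30% high grade and grade HR 3, crude power is 61% at OR 0.8 and 30% at OR 0.5. Stratified power is 77-80% over the settings examined.

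**4. Are these errors of the planned test?** In step 2 the two groups really do differ in survival, because they differ in grade. Rejecting is the right answer to the question of association that section II asks. The rates are errors only against a claim of value beyond grade, which the protocol does not make.

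**5. Would grade be missing from the Cox model?** Suppose grade is a candidate and a univariate p<0.05 screen is used. Its chance of entry is approximately Φ(√(d·p(1 − p))·ln h − 1.96), with d events and share p high grade. For d = 190 and h = 2:

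- p = 0.2: √30.4 × 0.693 = 3.82, so 96.9%
- p = 0.3: √39.9 × 0.693 = 4.38, so 99.2%
- p = 0.4: √45.6 × 0.693 = 4.68, so 99.7%

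At grade HR 3 or 6, with 15% or 30% events, grade passed in 99.8-100% of simulated studies. The weak corner is HR 2 with 15% events (about 95), where the formula gives 77% to 91%. There the leak is also small: at 30% high grade and OR 1.63 the shift is √95/2 × ln 1.082 = 0.38, a crude rejection rate of about 6.7%.

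**6. Would stratifying secure a claim beyond grade?** Not under this plan. If X-tile picks the best of 33 cut-points by the crude log-rank test (assumed use), the grade-stratified test on the chosen groups itself rejects in 15-31% of studies with no within-grade effect. That comes from the cut-off search and is a separate matter.

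**The case for a change.** The strongest case for a change is that it is cheap. Grade is recorded for everyone, two or three sentences would do, and stratifying cost no power in the settings simulated. Likely practice is not a commitment, and a Cox model meant to find prognostic factors will be read as adjusted evidence whatever it contains. With a strong link (OR 2.0, grade HR 6, 40% high grade) the crude test rejects in about 50% of studies against about 5% when stratified.

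The textual part stands: the covariates are unlisted and grade is not named among them. The rest carries less weight. The 50% figure comes from the far end of assumed inputs and describes a true crude association. A stratified log-rank test would largely repeat a grade-adjusted Cox model. Conditioning on grade also changes the question. Section I motivates the work by noting that grading information mostly becomes available only after surgery and histology, so what a pre-operative CT marker says before grade is known is a legitimate target. Grade may moreover lie on the path from body composition to survival, and adjusting for it would then remove part of the effect.

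**Conclusion.** No change to the plan is needed. The crude log-rank test fits the stated aim, and the search for prognostic factors is assigned to a multivariable Cox model. Leaving grade out of that model would be surprising in a protocol that calls grade prognostic. If grade is offered, it enters in about 97% or more of studies with 190 events and a grade HR of at least 2, so forcing it in would alter almost no result. What remains is an unlisted covariate set, a detail that analysts fill sensibly, and the ordinary caution that a crude curve is not evidence of independent value.

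The possible leak (crude rejection of 7-8% to 25-27% at the detectable link) rests on assumed event numbers, grade shares and hazard ratios. It also assumes that the log-rank groups are body-composition groups with a fixed cut-off, and it disappears if body composition is unrelated to grade. The judgement would differ if the protocol claimed prognostic value independent of grade.
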